### **5.0 INVESTIGATION PLAN**

#### **5.1 Summary**

See Section 10 for synoptic table.

Patients will receive decitabine 20 mg/m^2/day as a 1-hour infusion on consecutive days 1-10 of each 28-day cycle. Decitabine dose will be calculated on baseline weight (obtained within a week of the start of cycle 1). Decitabine dose should be recalculated for weight changes above or below 10% from baseline weight

Patients with clinical evidence of progressive disease or relapse (see Section 12 for definitions) should undergo a bone marrow biopsy to evaluate for progression.

After 2 cycles, patients with progressive disease or relapse (a clear progression with at least >20% bone marrow blasts and an increase of at least 50% from prior biopsy) should be removed from protocol and proceed to salvage treatment according to center preference.

Transplant eligible patients with PR after 3 cycles, may be removed from protocol and proceed to salvage treatment or transplant according to center preference.

Transplant eligible patients with a suitable donor who achieve mLFS, CR, CRc, or CRi, may proceed to transplant after at 3 cycles (Section 5.5).

Transplant ineligible patients with CR, CRc or CRi, PR will continue on maintenance doses (see below and Section 6.3) until progression or death, whichever occur first.

Transplant ineligible patient with SD after cycle 4 may be removed from protocol and proceed to alternative treatment or continue on protocol according to treating physician's preference.

After Cycle 1, patients with blast counts < 5% may reduce decitabine dose from 20 mg/m^2/day x 10 days to 20 mg/m^2/day x 5 days.

For all other patients, after Cycle 2, decitabine administration dose will be decreased to 20 mg/m^2/day for 5 consecutive days (Days 1-5) every 28 days (unless otherwise specified) to limit myelosuppressive toxicity.

Peripheral blood sampling and bone marrow biopsies with aspirate will be performed pre-study, on Cycle 1 Day 10 ± 2, Cycle 1 Day 28 ± 4, on Cycle 2 Day 28 ± 4, on Cycle 3 Day 28 ± 4, and at progression or relapse. Patients will provide a skin biopsy sample pre-study; a buccal swab can be performed for patients who decline skin biopsy. A buccal swab will be collected on Cycle 2 Day 28 ± 4.

Following Cycle 3, bone marrow biopsies should be performed at the discretion of the treating physician to assess for response and for relapse or progression.

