## 12.0 MEASUREMENT OF EFFECT

### 12.1 Response assessment

Bone marrow biopsy will be obtained on Cycle 1 Day 28 ± 4, Cycle 2 Day 28 ± 4, and Cycle 3 Day 28 ± 4. The cycle 2 Day 28 collection may be performed at the discretion of the treating physician.

All patients will be assessed for response according to the 2017 ELN AML Recommendations:

*Complete remission (CR)* – Defined as bone marrow blasts <5%; absence of circulating blasts and blasts with Auer rods; absence of extramedullary disease; absolute neutrophil count  $\geq 1.0 \times 10^9/L$  (1,000/ $\mu$ L); platelet count  $\geq 100 \times 10^9/L$  (100,000/ $\mu$ L).

*Complete remission with incomplete hematologic recovery (CRi)*: All CR criteria except for residual neutropenia -  $< 1.0 \times 10^9/L$  (1,000/ $\mu$ L) or thrombocytopenia -  $< 100 \times 10^9/L$  (100,000/ $\mu$ L)

*Cytogenetic complete remission (CRc)* – Defined as morphologic complete remission plus a reversion to a normal karyotype. For this study, reversion of a normal karyotype is defined as no clonal abnormalities detected in a minimum of 20 mitotic cells.

*Morphologic leukemia free state (mLFS)*: Defined as bone marrow blasts <5%; absence of blasts with Auer rods; absence of extramedullary disease; no hematologic recovery required. Marrow should not merely be “aplastic”; at least 200 cells should be enumerated or cellularity should be at least 10%

*Partial remission (PR)* – Defined as all hematologic criteria of CR; decrease of bone marrow blast percentage to 5% to 25%; and decrease of pretreatment bone marrow blast percentage by at least 50%.

*Stable Disease (SD)* – Defined as not meeting the definitions of CR, CRi, PR, PD, or recurrence/morphologic relapse.

*Progressive disease (PD)* – Defined as a clear increase in bone marrow blast count, typically a greater than 50% increase compared with baseline, or new extramedullary disease. Patients with a > 50% increase in peripheral blast count with an increase of the total peripheral white blood cell count to > 10,000/ $\mu$ l should undergo evaluation by bone marrow biopsy to assess for progressive disease. Patients enrolled with a bone marrow blast count < 20% will have > 20% blasts and a > 50% increase compared with baseline.

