*Recurrence/morphologic relapse* - Defined as relapse following complete remission is defined as reappearance of blasts in the blood or the finding of  $\geq$  5% blasts in the bone marrow, not attributable to any other cause. New dysplastic changes is considered relapse. If there are no blasts in the peripheral blood and 5-20% blasts in the bone marrow, bone marrow biopsy should be repeated in > 1 week to confirm relapse.

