#### **A. Duration of Response and Stable Disease, Treatment Failure, Overall Survival and Event-free Survival**

**Duration of overall response:** The duration of overall response is measured from the time measurement criteria are met for CR or PR (whichever is first recorded) until the first date that recurrent or progressive disease is objectively documented

The duration of overall CR is measured from the time measurement criteria are first met for CR until the first date that progressive disease is objectively documented.

**Duration of stable disease:** Stable disease is measured from the start of the treatment until the criteria for progression are met, taking as reference the smallest measurements recorded since the treatment started, including the baseline measurements.

Treatment failure is defined as death or failure to achieve a complete or partial remission following 4 cycles of therapy.

Overall survival is defined as the date of first dose of study drug to the date of death from any cause. Patients still alive at the time of the final analysis will be right-censored.

Event-free survival is defined as the interval from the date of first dose of study drug to date of treatment failure, recurrence, death due to any cause, or loss to follow up.

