## **E. Secondary Clinical Endpoints Analyses**

The principal measurement of toxicity will be a measure of the total number hospitalized days during the first 60 days of therapy.

**CRc rate** will be analyzed based on the ITT population. The remission rate and its 2-sided 90% confidence interval (CI) will be summarized.

**Event-free survival:** EFS will be analyzed using Kaplan-Meier methodology and Kaplan-Meier plots will be provided using the ITT analysis set. The median EFS and its 2-sided 90% CI using the complementary log-log transformation method (Collett 1994) will be calculated.

**Leukemia-free survival:** LFS will be analyzed using Kaplan-Meier methodology

and Kaplan-Meier plots will be provided using the ITT analysis set. The median LFS and its 2-sided 90% CI using the complementary log-log transformation method (Collett 1994) will be calculated.

**Time to leukemia relapse:** TTCR will be summarized using descriptive statistics.

The time to stem cell transplant, the proportion of patients who are able to undergo transplantation, and the average number of hospital days during cycles 1 and 2, will also be documented. The association between response and clinical characteristics (morphologically evident disease -i.e., >5% blasts by cytomorphology- versus molecularly detected disease at the time of enrollment -i.e., disease detected with flow cytometry, cytogenetic, or mutational analysis with  $\leq 5\%$  blasts by cytomorphology-, *de novo AML versus secondary AML versus treatment-related AML*, presence *versus* absence of cytogenetic abnormalities in addition to *TP53* mutations, etc.) will be described using contingency tables and compared by Chi-square test or Fisher's exact test as appropriate. The association between survival (OS, EFS, LFS) and clinical characteristics will be described using Kaplan-Meier methods and compared by log-rank test.

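### Event-free survival omits progressive disease, and 2-year EFS after transplant has neither a definition from transplant nor progression contacts scheduled to its landmark

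*Combined protocol and SAP*

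**What the plan says.** Section 12.1.A defines EFS as the interval from first dose "to date of treatment failure, recurrence, death due to any cause, or loss to follow up". Of these events, two need their own definitions:

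- Treatment failure: "Treatment failure is defined as death or failure to achieve a complete or partial remission following 4 cycles of therapy".
- Recurrence, in Section 12.1: "relapse following complete remission is defined as reappearance of blasts in the blood", or at least 5% marrow blasts. It applies only after complete remission.

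PD has a separate definition in Section 12.1. Section 12.1.A uses it for duration of overall response, which runs "until the first date that recurrent or progressive disease is objectively documented".

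On treatment, Section 5.1 says "Transplant ineligible patients with CR, CRc or CRi, PR will continue on maintenance doses" until progression or death. It says that patients with PD or relapse after 2 cycles "should be removed from protocol and proceed to salvage treatment according to center preference". On the Cycle 2 marrow, Section 12.1 says: "The cycle 2 Day 28 collection may be performed at the discretion of the treating physician".

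Section 15.4.E plans Kaplan-Meier plots of EFS on the ITT set, "The median EFS and its 2-sided 90% CI using the complementary log-log transformation method", and log-rank comparisons of EFS between clinical groups. It has no EFS analysis that starts at transplant, although item 5 of Section 2.2 asks for 2-year EFS after transplant against a historical 18-22%.

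Section 5.5 keeps patients on study through the day of transplant and then names follow-up for overall survival. Section 5.1.J records subsequent therapy, progression and death every 6 months for 2 years after the last dose. Section 5.9 sets a minimum of 2 years from enrollment.

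**The concern.** An EFS definition should give every patient who loses disease control an event, with a date. This one leaves two groups uncovered: patients who progress after PR, and patients with PD before the 4-cycle assessment. The first group is expected, because transplant-ineligible patients in PR stay on decitabine until they progress. A missing or late event can only lengthen EFS, so the error runs in the favourable direction. Two analysts could also obtain different medians from the same data, depending on how each dates an early failure.

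For Objective 5, the reader is promised a comparison with 18-22% at 24 months after transplant. The plan states no event list from that start, and it schedules progression contacts on a clock that starts earlier.

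**Working it through.** The plan states no figure for EFS, so there is none to reproduce. The check is a reading of the definitions, then arithmetic under stated assumptions. Months are 30.44 days, so day 56 = 1.84, day 84 = 2.76 and day 112 = 3.68 months.

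**1. Which patients have an event**

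| Course | Treatment failure? | Recurrence? | EFS ends at |
|---|---|---|---|
| CR, then relapse | no | yes | relapse |
| PR, then PD | no, PR was achieved | no, never in complete remission | death or loss to follow-up |
| PD after 2 cycles, removed | only as no CR/PR following 4 cycles | no | no date rule |

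Duration of response names recurrent and progressive disease separately, so the word recurrence in EFS cannot be taken to include PD.

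**2. Size of the gap for PD after PR**

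Assumptions: PR as best response in a share x = 5-15%; PD at a median of m = 2 or 4 months after day 84; exponential OS with 25% or 40% alive at 1 year (the null and alternative in Section 15.4.G); PD does not change the death rate.

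Overstatement at t months = x × OS(t) × [1 − 2^(−(t − 2.76)/m)].

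- 6 months, lowest: 0.05 × 0.50 × [1 − 2^(−3.24/4)] = 0.05 × 0.50 × 0.430 = 1.07 points.
- 6 months, highest: 0.15 × 0.632 × [1 − 2^(−3.24/2)] = 0.15 × 0.632 × 0.675 = 6.40 points.
- 12 months, lowest: 0.05 × 0.25 × 0.798 = 1.00 point.
- 12 months, highest: 0.15 × 0.40 × 0.959 = 5.76 points.

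Two variations reduce it:

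- If median survival after PD is only 2-4 months, numerical integration gives 0.7-5.3 points at 6 months and 0.3-3.1 at 12.
- If PR lost before the end of Cycle 4 counts as failure at day 112, the bracket becomes 2^(−0.92/m) − 2^(−(t − 2.76)/m). The gap is then 0.71-3.81 points at 6 months and 0.81-4.12 at 12.

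**3. Size of the dating effect for early PD**

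Assumptions: PD share p, found at day 56; stable disease share s = 0-40%, failing at day 112; the rest relapse at a median of 7 months after day 56; OS as above. Between day 56 and day 112:

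- PD dated when found: EFS(t) = OS(t) × [(1 − p − s) × 2^(−(t − 1.84)/7) + s].
- PD dated day 112: the same, with p added inside the bracket.

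Example with p = 20%, s = 0 and 25% 1-year OS. Dated when found, EFS(3.03) = 0.705 × 0.8 × 0.889 = 0.50, so the median is about 3.03 months. Dated day 112, EFS is 0.567 just before 3.68 months and 0.436 just after, so the median is 3.68. The difference is 0.65 months.

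| Assumed PD | Difference in median, 25% 1-year OS | 40% 1-year OS |
|---|---|---|
| 10% | 0 to 0.07 | 0 |
| 20% | 0.28 to 0.65 | 0 |
| 30% | 1.05 to 1.27 | 0.16 to 0.72 |
| 40% | 1.84 | 1.45 to 1.59 |
| 50% | 1.84 | 1.84 |

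Ranges are over s = 0-40%. If PD is found at day 84 instead, the difference at PD 40-50% is 3.68 − 2.76 = 0.92 months. EFS at 6 months does not change in any of these scenarios, because both dates precede it.

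**4. Progression contacts against the 24-month landmark**

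The last scheduled contact falls, in days after transplant, at last dose + 730 − transplant day.

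- Last dose Cycle 3 Day 5 (day 61), transplant day 84: 61 + 730 − 84 = 707, which is 23 days short.
- Last dose Cycle 4 Day 5 (day 89), transplant day 95-97: 724-722, which is 6-8 days short.
- Last dose day 61, transplant day 117: 674, which is 56 days short.

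The shortfall is 6-56 days, or about 1-8 weeks. It equals the time from last dose to transplant, for which the documents set no limit. On the Section 5.9 minimum, transplant about 11-17 weeks after first dose (marrow at Cycle 3 Day 24-32 plus an assumed 0-28 days of work-up) leaves a shortfall of the same 11-17 weeks.

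**The case against.** **Treatment failure already covers PD.** It may count early PD as an event, but it gives no date before the 4-cycle assessment, and it cannot reach PD after a PR that was achieved. It could be read as not being in CR or PR at the end of Cycle 4. That captures PR lost before then and shrinks the gap as shown, but later progression stays uncovered.

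**Progression dates are collected.** This stands. The Disease Assessment Form in Section 11 is due at progression and there is an Off Treatment Form, so an analyst could date failure then. A reader might infer that the plan dates early PD at day 112. It does not; that date is only an assumption used to size the ambiguity.

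**The PD and PR rates are assumed.** This also stands. Nothing in the documents supports a PD rate of 40-50%. PR needs full CR blood counts, and patients enrolled with 5% blasts or fewer have little or no room to meet its blast criteria.

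**Objective 5 is workable.** A reader might infer that it cannot be computed. That goes too far: its wording implies the start date, and recurrence and death carry over for patients transplanted in complete remission. Patients in morphologic leukemia-free state are less clear, since recurrence is defined only after complete remission. Nor is progression follow-up absent after transplant, because Section 5.5 does not cancel the contacts in Section 5.1.J.

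**The consequence is limited.** EFS from first dose is not among the Section 2.2 objectives. It is a descriptive median with subgroup log-rank tests in a single-arm trial.

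**Conclusion.** The definitions need correcting. Followed literally, the EFS event list omits progression after PR and leaves early PD undated, and both can only lengthen EFS. For PD after PR the overstatement is roughly 1-6 points at 6 and 12 months, given a 5-15% PR share, and smaller if PD shortens survival or if early loss of PR counts as failure. For early PD dated as late as day 112, the median moves by none to about 0.65 months at an assumed PD rate of 10-20%, and by more at higher rates. OS, the primary endpoint, is unaffected.

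Objective 5 lacks a stated definition and analysis from transplant. Its scheduled contacts end before 24 months whenever transplant follows the last dose. The direction is certain; the 1-8 weeks rests on assumed transplant timing and is not a bound.

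Two stronger inferences do not hold. EFS after PR and PD does not run on strictly until death, because loss to follow-up is also listed as an end point. And a reader might infer that only about a third of patients could reach the landmark by the final analysis. That assumes Objective 5 is reported at about 3 years, an estimate given in the interim analysis paragraph (Section 15.4.D) and not stated for this endpoint.

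**What to change.** - Define EFS as first dose to the first of: documented PD under Section 12, dated at documentation; no CR or PR after 4 cycles, dated at that assessment; relapse; or death from any cause. State that loss to follow-up is censored at the last disease assessment.
- Define post-transplant EFS separately, from transplant date to relapse, progression or death, and add its analysis to Section 15.4.E.
- For transplanted patients, continue the existing 6-monthly contacts to 24 months after transplant.

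The cost is a wording amendment, about one extra contact per transplanted patient, possibly later reporting of one secondary endpoint, and possibly a less favourable EFS.

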#### **B. Duration of Remission and Relapse-free Survival for Patients Having Complete Remission**

Duration of complete remission is defined as the interval from the date that complete remission is documented to the date of recurrence, death due to any cause, or loss to follow-up.

Relapse-free survival is defined only for those patients achieving a CR or CRi. It is defined as the interval from the date of first documentation of a leukemia-free state to the date of recurrence, death due to any cause, or loss to follow up.

### **13.0 DATA AND SAFETY MONITORING**

In compliance with the Washington University Institutional Data and Safety Monitoring Plan, an independent Data and Safety Monitoring Board (DSMB) will be specifically convened for this trial to review toxicity data. . A DSMB will consist of no fewer than 3 members including 2 clinical investigators and a biostatistician. DSMB members must be employed by Washington University, Barnes-Jewish Hospital, or St. Louis Children's Hospital. Like investigators, DSMB members are subject to the Washington University School of Medicine policies regarding standards of conduct. Individuals invited to serve on the DSMB will disclose any potential conflicts of interest to the trial principal investigator and/or appropriate university officials, in accordance with institution policies. Potential conflicts that develop during a trial or a member's tenure on a DSMC must also be disclosed.

Until such a time as the first secondary site enrolls its first patient, a semi-annual DSM report to be prepared by the study team will be submitted to the Quality Assurance and Safety Monitoring Committee (QASMC) semi-annually beginning six months after study activation at Washington University (if at least one patient has been enrolled) or one year after study activation (if no patients have been enrolled at the six-month mark).

The DSM report for the DSMB will be prepared by the study team with assistance from the statistician, will be reviewed by the DSMB, and will be submitted to the Quality Assurance and Safety Monitoring Committee (QASMC). The DSMB must meet at least every six months beginning six months after study activation at Washington University or beginning six months after enrollment of the first patient at a secondary site, no more than one month prior to the due date of the DSM report to QASMC. This report will include:

- HRPO protocol number, protocol title, Principal Investigator name, data coordinator name, regulatory coordinator name, and statistician
- Date of initial HRPO approval, date of most recent consent HRPO approval/revision, date of HRPO expiration, date of most recent QA audit, study status, and phase of study
- History of study including summary of substantive amendments; summary of accrual suspensions including start/stop dates and reason; and summary of protocol exceptions, error, or breach of confidentiality including start/stop dates and reason
- Study-wide target accrual and study-wide actual accrual including numbers from participating sites
- Protocol activation date at each participating site
- Average rate of accrual observed in year 1, year 2, and subsequent years at each participating site
- Expected accrual end date and accrual by site
- Objectives of protocol with supporting data and list the number of participants who have met each objective

- Measures of efficacy
- Early stopping rules with supporting data and list the number of participants who have met the early stopping rules
- Summary of toxicities at all participating sites
- Abstract submissions/publications
- Summary of any recent literature that may affect the safety or ethics of the study

Further DSMC responsibilities are described in the DSMC charter.

Until such a time as the first secondary site activates this protocol, a semi-annual DSM report to be prepared by the study team will be submitted to the QASM Committee beginning 6 months after study activation at Washington University.

The study principal investigator and coordinator will monitor for serious toxicities on an ongoing basis. Once the principal investigator or coordinator becomes aware of an adverse event, the AE will be reported to the HRPO and QASMC according to institutional guidelines (please refer to Section 7.0).

Refer to the Washington University Quality Assurance and Data Safety Monitoring Committee Policies and Procedures for full details on the responsibilities of the DSMC at <https://siteman.wustl.edu/wp-content/uploads/2015/10/QASMC-Policies-and-Procedures-03.31.2015.pdf>

## **14.0 AUDITING**

As coordinating center of this trial, Washington University (via the Quality Assurance and Safety Monitoring Committee (QASMC)) will monitor each participating site to ensure that all protocol requirements are being met; that applicable federal regulations are being followed; and that best practices for patient safety and data collection are being followed per protocol. Participating sites will be asked to send copies of all audit materials, including source documentation. The audit notification will be sent to the Washington University Research Patient Coordinator, who will obtain the audit materials from the participating institution.

Notification of an upcoming audit will be sent to the research team one month ahead of the audit. Once accrual numbers are confirmed, and approximately 30 days prior to the audit, a list of the cases selected for review (up to 10 for each site) will be sent to the research team. However, if during the audit the need arises to review cases not initially selected, the research team will be asked to provide the additional charts within two working days.

Items to be evaluated include:

- Subject screening and enrollment
- Reporting of adverse events
- Maintenance of HIPAA compliance
- Completeness of regulatory documentation
- Completeness of participant documentation

- Acquisition of informed consent
- IRB documentation
- Issues of protocol adherence

Additional details regarding the auditing policies and procedures can be found at <https://siteman.wustl.edu/wp-content/uploads/2015/10/QASMC-Policies-and-Procedures-03.31.2015.pdf>

